# 12. Ancillary sub-studies

## 12.1 Embedded process evaluation

In order to understand participant experience and the implementation process (including barriers and facilitators to implementing the new intensive NIV initiation service), a mixed-methods embedded process evaluation will be conducted in accordance to the MRC framework[41]. The primary focus is on implementation outcomes. Quantitative data on NIV usage from participants ventilators will provide clinical context to interpret the implementation findings.

#### 12.1.1 Aims

The process evaluation will aim to understand the following:

- 1. What is implemented at sites and how the intervention was delivered?
- 2. How does context affect implementation and outcomes, including staff and patient participants experiences?
- 3. How did the effects of each intervention occur (mechanisms of impact) and whether these were in line with the expected programme theory set out earlier in the protocol?

#### 12.1.2 Objectives

- 1. Use the NOMAD survey to understand barriers and facilitator pre and post implementation delivery, in both champions and the wider clinical team.
- 2. Conduct semi-structured interviews with site staff based on CFIR, to understand barriers and facilitators of the implementation intervention within the healthcare setting.
- 3. Conduct semi-structured interviews with participants and family members/friends to understand their experiences of the intervention.
- 4. Assess fidelity of the intervention against the programme theory:
  - a. Use quantitative telemonitoring data to identify engagement from site staff
  - b. Assess the intervention fidelity by examining 10% of staff worksheets for completeness.
  - c. Assess intervention fidelity by observing n=24 participants / staff interactions within clinical consultations
  - d. Conduct observations of multidisciplinary team meetings to examine the delivery of the intervention and its impact on the wider team's behaviour.

#### **12.1.2 Methods**

A multiple-case design will be used to capture the variation in intervention delivery across sites, explore participant responses to the trial, and barriers and facilitators to implementing the intervention. This will be conducted in all 12 sites. This will document the conditions that are necessary for goal-based approach to NIV to be normalised and obtain the perspective of professionals directly involved in intervention implementation, supporting trial recruitment and supporting participants and their families.

During the control arm phase, all sites will complete the NOMAD questionnaire[42]. Site assessment forms may also be used to provide local context prior to the intervention. Recruitment to the process evaluation interviews and observations will begin once a site switches on to the intervention. Data collection will not occur in the first 4 weeks of a site using the intervention. The NOMAD questionnaire will be completed again six months after switching to the intervention arm. We will supplement data collection with study management logs such as site assessment forms. To inform the fidelity assessment we will audit 10% of worksheets for completeness.

#### Sampling

Patient participants: Patients will be recruited to participate in both observations and interviews where possible. Purposive sampling will be conducted based on predefined participant diversity criteria, including ethnicity, gender, age, disease severity, NIV use at 4 weeks and digital health literacy levels,

completed at baseline. We will examine participant characteristic lists to identify potential participants for contact. We will collect sociodemographic characteristics of participants to enable us to monitor inclusivity and respond if necessary.

We will formally monitor recruitment monthly to ensure that participants with a range of characteristics are being recruited. This will be conducted by EH, AG, CG and the post-doctoral researcher. Additionally, a three-monthly report will be presented to the TMG for reflection and advice on future recruitment. Per site, 1-2 patients will be recruited (up to 24 in total) alongside their family members (approximately 24 in total). Patients can participate without a family member agreeing to consent. Where more than one family member is identified, the patient can identify who they wish to be involved in each interview/observation, ideally someone who is supporting the patient to use NIV. We will obtain consent from family members as they become involved in the process evaluation.

Site participants: Alongside these participants, staff members (n=2 per site) will be recruited to participate in interviews. We will strive to recruit staff members with a range of roles, years of experience working with people with MND, and demographic characteristics. Participants will complete consent forms to participate in interviews, and will be asked to opt-out of observations, rather than providing consent.

Site staff NOMAD survey: We will sample staff who are both actively delivering NIV care and staff with supporting roles.

#### Patient participant eligibility criteria

- 1. Have consented to participate in DENIM
- 2. Are in the intervention arm
- 3. Are able and willing to participate in interviews (various options for facilitation available) and/or ethnographic observations
- 4. If relevant, are willing to share their preferred language for participation with the research team, to allow an appropriate researcher to be identified.

#### Relative/friend eligibility criteria

- 5. Relative/friend has consented to participate in DENIM
- 6. Are able and willing to participate in interviews and/or ethnographic observations
- 7. If relevant, are willing to share their preferred language for participation with the research team, to allow an appropriate researcher to be identified.

## Staff interview eligibility criteria

8. Direct contact with at least one patient who is participating in DENIM

9. Are able and willing to participate in interviews and/or ethnographic observations

#### **Qualitative Interviews**

An experienced qualitative researcher will conduct semi-structured interviews framed around CFIR and NPT[22] with staff (n=1-2 per site at two timepoints, schedule as per observations) and patients/carers (n=24, 1-3 per site).

Written informed consent will be obtained from all participants where possible. Where a participant is unable to sign their name, a witness will be identified to witness their consent process. Verbal consent will be obtained before all interviews begin.

Informed consent procedures will be completed before any data is collected and will cover agreement to participate in a) semi-structured interviews, b) ethnographic observations, or c) both. Prior to each interview or observation, consent will be reobtained verbally. Consent will be confirmed on the interview recording, or in observation field notes.

## Patient and family member/friend interviews

Patients and family members/friends can choose to participate in interviews separately or together. A topic guide will be developed and examples from observations will be used to stimulate discussion. Interviews will be conversational in nature, following the lead of the participant and their communication preferences. Adjustments include use of email, telephone, video or face-to-face interviews, use of proxies, interpreters and communication devices, use of NIV during the interview, frequent breaks. Participants can decline to answer any questions, to end the interview at any time, and can withdraw their data without providing reasons. Interviews will be approximately 30-60 minutes, dependent on what participants wish to say and their preferred interview pace. Interviews will be audio-recorded and transcribed verbatim.

Informal conversations will be offered to participants who may struggle to participate in semi-structured interviews, so they are able to share experiences. Rather than being arranged separately, these will be conducted shortly following the conclusion of observations, where possible, while the participant is still in the clinic setting. We will supplement this data with data from medical records regarding NIV related care (e.g. letters, reports on appointments), where participants consent to this have been involved in observations (1-2 per site).

Where paid social care professionals (e.g. personal assistants) are included in interviews if they are present to support the patient participant, they should provide consent. Individuals present purely to support patient participants who do not consent will have their data removed following transcription.

# 12.1.3 Ethnographic observations

We will conduct focused ethnography[43] with two patients-staff interactions per site (n=24 total), observing their experiences and interactions with staff around initiation and use of NIV. Prior to patient recruitment, researchers will conduct familiarisation observations of MDT meetings and broader clinic discussions and observe staff training sessions at up to four sites. This will enable familiarisation with usual care practices within the site. Staff will be informed about the observations through posters in their clinic settings, and given the opportunity to opt out having their patient interactions observed.

Appointment observations will be conducted with patients in their NIV initiation appointment (we anticipate this will be approximately four to six weeks following the start of site intervention adoption) and may include other NIV-related conversations that are planned by clinicians. We will ask both the patient and clinician to confirm the date and time of the appointment, which the researcher will attend. We anticipate spending around two to three hours with each patient, spending time with them whilst they're in the waiting room, during the appointment, and any time after the appointment in the waiting room. Posters will be placed around areas that observations will take place in, and staff will be recruited on an opt-out basis.

We will also observe an appointment within the last eight weeks of the study during which time the staff will review the telemonitoring data and (as required) communicate with the patient/carer/MND MDT to act upon any decisions being made. We will ask both the patient and clinician to confirm the date and time of the appointment with the research team.

Observation field notes will include conversations and non-verbal behaviours i.e. body language, and communication between participants, focusing on decision-making, barriers and facilitators to NIV initiation and use, and any identified care needs. The researcher will be a non-participant observer who will attend in person and sit in the corner of the appointment room without contributing to the discussion. Following appointments, researchers will engage in informal conversations with people with MND and their carers to further explore observed experiences. These conversations will take place in confidential spaces, such as the appointment room or another room within the NHS Trust building. We will adapt the format of observations and informal conversations to the abilities and preferences of participants, i.e. their favoured communication method.

# 12.2 Analysis

Ethnographically informed thematic analysis will be used to conduct line-by-line coding to develop an initial coding framework, drawing together data from observation field notes, informal conversations, medical records, and interviews together. We will analyse multiple sources of data from each individual together where possible (see Data Triangulation below).

Data interpretation will be iterative, building on data collected in WP1. Each interview/focus group transcript and set of field notes will be independently coded and analysed by two researchers, before being applied to the framework. Codes and themes will be compared across participants and sites, to develop a contextualised understanding, incorporating any changes over time. We will explore verbal and non-verbal interactions between participants. PPI representatives will work alongside us to develop and refine themes in smaller group discussion sessions. Staff data will initially be analysed separately to those with people with MND and carers, before the developed themes will be compared and contrasted to produce definitive themes. These themes will be finalised through review and discussion. Analysis will be conducted concurrently with data collection, to monitor data quality and inform subsequent data collection.

# Data triangulation

Each case will have four embedded units of analysis; the three aspects of the process evaluation (interviews, ethnographic observations, staff survey), alongside NIV-use data from participants ventilators. We will deductively code ethnographic field notes and interview transcripts to NPT constructs, with a small group of the research team (EH, AG, CM), before sharing this with the wider team. We will then conduct a cross-case framework analysis[44], integrating the results with NoMAD / NIV-use statistics in joint display tables[45]. Differences/changes in adherence will be compared across sites and in relation to measures of normalisation (NoMAD) and site characteristics (caseload, current standard of care) to understand how the programme's efficacy depends on aspects of context. This will identify specific strategies that could improve adherence to the intervention protocols and procedures. We will then share these strategies with those monitoring data quality and across sites, to help improve adherence.

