#### 13.2 Data Monitoring and Ethics Committee

The Data Monitoring Ethics Committee (DMEC) will consist of an independent statistician, and a independent physicians. There will be no interim analyses other than to confirm the internal pilot / stopping guidelines, but the DMEC will be able to request data and recommend study termination to the TSC/funder on grounds of safety or futility. The DMEC will meet every six months from the start of the trial to review reports provided by the CTRU and assess the progress of the trial.

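### Process-evaluation strategies are to be shared across sites during a stepped wedge, with no limit to sites that have already switched

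*Protocol*

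**What the plan says.** The Data triangulation paragraph of section 12.2 describes a cross-case analysis, "integrating the results with NoMAD / NIV-use statistics in joint display tables". It continues: "Differences/changes in adherence will be compared across sites and in relation to measures of normalisation (NoMAD) and site characteristics". The stated product is: "This will identify specific strategies that could improve adherence to the intervention protocols and procedures". The next sentence sets out what happens to it: "We will then share these strategies with those monitoring data quality and across sites, to help improve adherence".

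On timing, the thematic-analysis paragraph of section 12.2 says: "Analysis will be conducted concurrently with data collection, to monitor data quality and inform subsequent data collection". The Data triangulation paragraph itself gives no date.

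On recipients, no section sets a limit by trial phase. Section 12.1.2 (Methods) opens interviews and observations only once a site has switched, but that governs where data are collected, not who receives the lessons. Section 6.2.4 lets new techniques spread through local champions and is also silent on phase.

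Sections 4 and 7 give the schedule: a six-month roll-in with all 12 sites in usual care, then two sites switching every three months in random order.

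**The concern.** A stepped wedge estimates the effect by comparing switched sites with sites still in usual care in the same period. It needs the unswitched sites to remain in usual care until their randomised date. Sections 6.2 to 6.2.3 describe an intervention made up mainly of training, review routines, coaching and peer support. Advice on making it work is therefore a piece of the intervention itself. If that advice goes to all sites, some control-phase patients receive part of the treatment and the contrast shrinks.

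The protocol protects this separation elsewhere. Section 9 sends ventilator data to the clinical team in the intervention arm only. The sharing sentence carries no matching safeguard.

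**Working it through.** **Inputs.** Section 11.1: SD 10 days (printed with a typographical slip), difference 6 days, ICC 0.05, two-sided 5%, 15% drop-out, three patients per site in the roll-in and one per month in months 7 to 24. Sections 4 and 7: 12 sites, two switching at each of months 6, 9, 12, 15, 18 and 21, so 7 periods. Assumed, because the protocol gives no figure: leakage of L days in control-phase patients, and the month it starts.

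**The plan's own figures.** Recruitment: 12 × (3 + 18) = 252. Analysed: 252 × 0.85 = 214. There are 12 × 7 = 84 site-periods, so 3 recruited and 2.55 analysed in each. I used a linear mixed model with fixed period effects and a random site effect. The covariance of the period means within a site is V = diag(σ²(1 − ρ)/m) + σ²ρJ, with σ = 10, ρ = 0.05, m = 2.55 and J a matrix of ones. Generalised least squares gives SE = 2.007 days and power Φ(6/2.007 − 1.96) = 84.8%. With m = 3 (all 252 analysed) the power is 89.4%. The stated 90% is therefore matched closely only without drop-out. That is a separate matter and does not bear on this point.

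**Who is exposed.** Control site-periods: 12 in the roll-in, then 10, 8, 6, 4, 2 and 0, in total 42, or 42 × 3 = 126 recruited controls. After the roll-in: 30 site-periods, 90 controls. From month 12: 6 + 4 + 2 = 12, or 36 controls. From month 15: 4 + 2 = 6, or 18 controls. From month 18: 2, or 6 controls.

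**When leakage could start.** The second NoMAD is due six months after a site switches (section 12.1.2, Methods). The first pair switches at month 6, so its repeat survey falls at month 6 + 6 = 12. Month 12 is therefore an early start for strategies that draw on post-switch NoMAD, and it allows no time for coding and synthesis. Months 15 and 18 allow for some delay.

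**Expected estimate.** Add L to the affected control cells and refit. The result is linear: expected estimate = 6 − kL, where k depends on the start. Power = Φ(estimate/2.007 − 1.96).

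| Leakage from | Controls affected | k | L = 1 day | L = 1.5 days |
|---|---|---|---|---|
| Month 12 | 36 of 126 | 0.629 | 5.37 days, power 76% | 5.06 days, power 71% |
| Month 15 | 18 of 126 | 0.371 | 5.63 days, power 80% | 5.44 days, power 77% |
| Month 18 | 6 of 126 | 0.143 | 5.86 days, power 83% | 5.79 days, power 82% |

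Power without leakage on the same model is 85%. At month 12, k exceeds the share of controls affected (36/126 = 29%). With step in the model, the estimate leans on periods in which switched and unswitched sites run side by side, and the affected cells lie in those periods. The model is linear, whereas section 11.2.2 plans a Poisson mixed model, so the figures show direction and rough size only.

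**The case against.** The strongest reply is that the shared strategies concern fidelity, not wear time. The sentence just before the sharing sentence says so ("This will identify specific strategies that could improve adherence to the intervention protocols and procedures"), and a control-phase site has no DENIM procedures to follow. On that reading the natural recipients are sites already delivering the intervention. This is a fair account of the likely intent, and it makes the exposure one of missing wording. It does not supply the limit, and a site that follows the sentence literally would not know the limit exists.

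A second reply is that the timing is inferred. The concurrent-analysis sentence belongs to the qualitative work, and the last pair's repeat NoMAD falls at about month 21 + 6 = 27, so the full cross-case analysis must finish late. That stands for the complete analysis. It does not rule out partial feedback earlier, and strategies to improve delivery are useful only while sites are delivering.

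Two stronger readings are tempting and are not supported:

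- A reader might infer a contradiction with section 13.2 ("There will be no interim analyses other than to confirm the internal pilot / stopping guidelines"). That sentence stands in the data monitoring committee section, beside termination for safety or futility, and most naturally governs formal interim analyses. The triangulation paragraph plans joint displays of NIV use against NoMAD and site context, with no stated test of the treatment effect and no stopping decision. At most the two are unreconciled.
- A reader might object to teams reacting to outcome data at all. In the intervention phase that is the treatment: sections 2.2, 6.2.2 and 9 have clinical teams review wear time and act on it. Holding back every NIV-use comparison until data lock would be a real loss to a type 3 hybrid trial, and the documents do not require it.

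**Conclusion.** The point holds as a gap in wording with a plausible route to bias. The protocol commits to sharing strategies across sites and nowhere limits this to switched sites, while some sites remain in control until month 21. Any leakage that raises control-phase wear time would bias the effect towards zero. Its size is unknown. With an assumed 1 to 1.5 days, the expected estimate is 5.4 to 5.1 days if leakage starts at month 12, and 5.6 to 5.4 days if it starts at month 15, against a true six days. A month-18 start would cost about 0.2 days or less. These figures rest on the assumed leakage, on every control-phase site being affected equally from the start month, and on the linear model with the section 11.1 inputs. A start before month 12 is hard to defend, because no site would yet have its six-month NoMAD.

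**What to change.** Amend the sharing sentence under Data triangulation so that, until the last sites have switched, strategies go only to sites already delivering the intervention, and each later site receives them at its own switch. At most, add that site-level NIV-use summaries produced before data lock are descriptive and make no comparison between intervention and control phases.

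The cost is one clause, or two sentences with the optional addition. Late-switching sites receive the lessons later than they otherwise might. The process evaluation keeps all its data sources and its in-trial feedback to switched sites.

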# 12.3 Accessing Care and Clinical Engagement in Support Services for NIV (ACCESS sub study)

Equality, diversity and inclusion research embedded within the process evaluation

Research question

What are the barriers and enablers to effective recruitment, retention and engagement of participants from underserved MND populations and how might these be addressed?

#### **Aim**

To investigate the participants' experiences of barriers and enablers, and intersectional factors (e.g., culture, ethnicity, socioeconomic status) that influence participation in DENIM. We will also speak to participants least likely to participate in MND clinical trials and/or who face the most difficulties receiving the proposed intensive NIV initiation. We will also explore to what extent our EDI component helped facilitate or hinder participation, to make recommendations for this trial and for future trials of complex interventions in long-term neurological conditions.

#### Inclusion criteria

The study will purposefully sample participants known to be less likely to participate in MND research or gain value from NIV:

- From an ethnic minority and/or where the patient's main language is not English
- Or with low levels of digital health literacy (either those identified by the site teams or those scoring <7 on the 3-Item Measure of Digital Health Care Literacy) [52]

- Women over 80 with bulbar onset disease

